**OBJECTIVES**

STU00217126  
EH22-021

**Aim 1: Integrate routine clinical tests with PRO assessment to enhance screening, diagnosis, and management of patients with Benign Prostatic Hyperplasia (BPH).** PROs provide a cost-effective assessment strategy that can improve patient care by allowing for frequent surveillance and intervention. Men with BPH suffer from a variety of comorbid conditions (e.g., sleep disturbance, depression). We will use longitudinal modeling to identify risk factors and comorbidities that predict increased LUTS. Specifically, we will use PROs, developed by us in the LURN, to assess LUTS, including symptoms not captured by AUA-SI. We hypothesize that health variables from the PROMIS-29 Profile (e.g., sleep disturbance, depression, pain), when combined statistically with routine objective clinical variables (e.g., uroflowmetry, prostate size, intravesical prostatic protrusion) will provide unique predictive power for LUTS severity over time. Understanding these risk factors will facilitate preventative counseling and "just-in-time" interventions to improve in-clinic and telemedicine evaluations and treatment.

**Aim 2: To examine psychometric properties of the LURN SIs, including clinically meaningful differences in men with BPH receiving known effective treatment.** Longitudinal data will enable us to calculate effect sizes of the SI-10 and SI-29 from baseline to follow-up in the context of usual care, including guideline-driven treatment of BPH. LURN SIs will be anchored to patients' ratings of global change (PGI-I). A multiple-baseline design will allow estimation of test-retest reliability, while multiple longitudinal assessments provide quantitative estimates of minimally important differences (MIDs). We hypothesize that the SI-10 and SI-29 will have adequate test-retest reliability and precision to detect change across a range of severity in BPH in response to treatment.

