### **STUDY ENDPOINTS:**

Aim 1: Longitudinal trajectories of LUTS in men treated for BPH. Serial symptom data will be collected over time using the LURN SI-29 (which includes the LURN SI-10 items) and the AUA-SI. Aim 1 will identify health variables from the PROMIS-29 Profile that predict trajectories of LUTS within the individual patient.

Aim 2: Test-retest reliability and minimally important differences in the LURN SI-29 subscales and the LURN SI-10. At the end of this study, we will have established the test-retest reliability of the LURN SI questionnaires and established minimally important differences in patients with BPH after known effective treatments.

Aim 3: A care-coordination checklist for monitoring of men treated for BPH. The goal of this project is to engage men with BPH and collect their open-ended input as to what symptoms, concerns, and challenges they face over the course of their treatment with BPH. In addition, 20 clinicians

STU00217126  
EH22-021

will also be interviewed. The end product will be transcripts from up to 40 men with BPH and 20 clinicians, and an accompanying code book.

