We created a battery of health measures to be specific to the management of BPH. The clinician will determine, on a case-by-case basis, the assessment schedule based on medical need, but sample schedules are presented in Tables 2.1 and 2.2 (medical management Table 2.1; surgical management Table 2.2). If a clinical follow-up visit is not required as part of standard of care as determined by the patient's personal physician (i.e., at Week 12 and Week 24 for medically managed patients), the follow-up visits can be completed remotely by phone, web, or app. Using PROs is already part of the management guidelines for BPH; the overarching hypothesis of this project is that a brief (i.e., clinically feasible) set of questions can aid in the management of BPH and can improve upon the existing method of the AUA-SI. We recognize that the proposed battery of measures is much longer than the one-page AUA-SI, but a longer battery of questionnaires is necessary for research purposes to clarify which measures would need to be dropped versus retained for use in the real-world clinic. In addition, scores from the one-page LURN SI-10 can be extracted from the longer 29-item questionnaire. Data analyses (see Section 1.4) will also include the LURN SI-10 score for maximum clinical relevance. Patients undergoing surgery will have more frequent queries in the immediate postoperative period (Table 2.2), as many men report bothersome symptoms of frequency, urgency, pain, and/or incontinence in this timeframe; thus, this period in particular is a target for better characterization and management of symptoms. We have had success with collecting data every 2 weeks as part of other research, supporting feasibility. Routinely collected objective clinical data, including urinalysis, prostate-specific antigen, uroflowmetry, post-void residual, prostate size, intravesical prostatic protrusion, and cystoscopic findings will also be collected and analyzed in combination with PROs.

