Note: Study time points (e.g., Week 4, Week 8) are approximate – Participants will be given a time window of $\pm$ 2 weeks. The minimum time between assessments will be approximately 4 weeks. Time windows may be adjusted based on COVID-19 protocols (e.g., if a clinic visit is converted to telehealth).									

STU00217126  
EH22-021**Table 2.2 Study questionnaires, surgical/procedural intervention  
(Schedule of assessments: baseline, inter-visit follow-up, and clinic assessments)**

	# Items	Baseline (clinic)	Preop **	Week 1	Week 2	Week 4 (clinic)	Week 6	Week 8	Week 12 (clinic)	Week 24 (clinic)
LURN SI-29	28									
PROMIS-29 Profile	29									
AUA-SI	8									
Patient Global Impression of Improvement (PGI-I)	1									
National Cancer Institute Quick Food Scan	17									
3-Day Voiding Diary	9									
PROMIS-GI: Constipation	9									
PROMIS-GI: Diarrhea	6									
SHIM	5									
MSHQ-EjD	4									
STOP-BANG	8									
PRO Cognitive Function – Short Form 4a	4									
Patient Feedback Survey (optional)	6									
Note: Study time points (e.g., Week 4, Week 8) are approximate – Participants will be given a time window of $\pm$ 2 weeks. The minimum time between assessments will be approximately 4 weeks. Time windows may be adjusted based on COVID-19 protocols (e.g., if a clinic visit is converted to telehealth). ** If surgery is not immediately scheduled, complete questionnaires every 4 weeks until surgery is scheduled.										

To assess MIDs, we will administer the PGI-I as a measure of global change at each post-baseline time point. The PGI-I is a single-item questionnaire that asks respondents to rate their condition compared with prior to treatment on a 7-point scale from very much worse (1) to very much better (7). LURN SI-29 and SI-10 scores at 12 weeks post-baseline will be used to assess changes in scores since baseline.

In addition, participants will be offered the opportunity to complete a patient-response burden questionnaire (patient feedback survey) at the end of their study participation. This will provide a better understanding of how the participants perceived the PROs.

STU00217126  
EH22-021

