**Uroflowmetry.** Uroflowmetry is a test that measures the flow rate of urination while the patient is voiding. It also quantifies the voided volume. Uroflowmetry is usually captured during routine care with a urologist, but sometimes it is not deemed necessary or logistically challenging to obtain during routine clinical care (for example, the patient voids before being seen in clinic). In this study, if the patient does not receive a uroflowmetry test as part of routine care, we may include it as a research activity. In this case, the patient will receive instructions from the research coordinator on how to do the test. To ensure that the patient does not have an empty bladder for the test, the coordinator will ask the patient to drink some water from water bottles provided in the clinic space, while the study is being explained to them. If possible, the patient will be asked not to void until the uroflowmetry test. They will then do the test in a private restroom at the clinic. For uroflowmetry, the patient simply voids into a funnel which measures voided volume and urine flow rates. At the end of the test, a printed readout is produced, which will be stored in a locked filing cabinet. A bladder scan (handheld ultrasound) may then be performed to measure the post-void residual volume. The research coordinator will enter the necessary values from the printed report into REDCap. There are no risks associated with uroflowmetry, as it involves voiding of urine. The test takes less than 5 minutes to complete.

The data set from the LURN I study, funded by the NIDDK, will be used as a comparator dataset: it will be incorporated into the visualization graphs to offer a comparative baseline and will also be utilized to compare and contrast findings from our study data.

**Crossover between treatment management arms:** If a participant in the medical management arm decides to undergo surgery during their routine clinical care, they are allowed to switch to the surgical management arm. At that point, the participant's timeline is restarted based on the treatment type. Similarly, participants enrolled in the surgical management arm that do not complete surgery will be moved into the medical management arm if they are using medical treatment.

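### The MID score change runs from study baseline, but its PGI-I anchor asks about change since before treatment, and the protocol does not make these the same point

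*Protocol*

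**What the plan says.** The rule stands in the Protocol, Procedures Involved, in the text after Table 2.2. It has three parts.

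- Anchor timing: "To assess MIDs, we will administer the PGI-I as a measure of global change at each post-baseline time point".
- Anchor reference: the PGI-I "asks respondents to rate their condition compared with prior to treatment on a 7-point scale".
- Score change: "LURN SI-29 and SI-10 scores at 12 weeks post-baseline will be used to assess changes in scores since baseline".

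Aim 2 under Objectives says that the LURN scores are anchored to the PGI-I. Study Endpoints promises "established minimally important differences in patients with BPH after known effective treatments".

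Other sections bear on when treatment starts relative to baseline:

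- The footnote to Table 2.2 says: "If surgery is not immediately scheduled, complete questionnaires every 4 weeks until surgery is scheduled". No upper limit is set on the wait.
- Study Timelines counts the 24 weeks of follow-up from baseline or treatment start, whichever is later.
- Recruitment Methods makes both new patients and returning patients under treatment eligible. Inclusion criterion 3 of the primary study asks for treatment that is planned.
- The compensation table for Endeavor Health labels the 12-week visit as post-treatment in the medical arm and post-procedure in the surgical arm.
- For men who change arm, the "timeline is restarted based on the treatment type".

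**The concern.** An anchor-based MID reads the score change among men who report a given amount of global change. It can be interpreted only if score and anchor describe the same interval. Here the score interval starts at study baseline and the anchor interval starts before treatment. If those are different dates, a man's PGI-I rating and his score change answer different questions. A larger sample does not remove the discrepancy.

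The MID is a named Aim 2 endpoint, and later users would rely on it to decide what change in LURN SI-10 or SI-29 matters to a patient.

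**Working it through.** The protocol gives no sample size, power or numerical target for the MID, so there is no figure to reproduce. The check compares the two reference points for each order of baseline and treatment. The delay, the share already treated and the timing of their gain are assumed throughout, because the protocol gives none of them.

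**1. Treatment starts at baseline.** Both reference points coincide and there is no problem.

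**2. Surgery after baseline.** Let D be the weeks from baseline to surgery. On the literal wording, weeks since surgery at the MID assessment = 12 − D, with the ±2-week visit window from the table notes:

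| D (assumed) | Weeks since surgery | With window |
|---|---|---|
| 0 | 12 | 10 to 14 |
| 4 | 8 | 6 to 10 |
| 8 | 4 | 2 to 6 |
| 12 | 0 | −2 to 2 |
| 16 | −4 | −6 to −2 |

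From D = 12 the nominal assessment falls on or before the day of surgery. The anchor then has no surgical treatment to refer to.

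On the other reading, Week 12 is counted from the procedure. The compensation table, the Study Timelines clock and the postoperative layout of Table 2.2 support this. The assessment is then 12 weeks after surgery for everyone. The remaining mismatch is any change in symptoms between Baseline and Preop, and its direction is unknown.

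**3. Treatment before baseline.** Let G be the mean gain since before treatment among men at the PGI-I level used for the MID, assumed equal in newly treated and already-treated men. Let s be the share already treated at baseline, and f the share of their gain made before baseline. Then

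measured mean change = (1 − s)G + s(1 − f)G = G(1 − sf),

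so the ratio of measured to true MID is 1 − sf:

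| s (assumed) | f = 25% | f = 50% | f = 100% |
|---|---|---|---|
| 10% | 0.975 | 0.95 | 0.90 |
| 25% | 0.9375 | 0.875 | 0.75 |
| 50% | 0.875 | 0.75 | 0.50 |

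If s is under 10%, the shortfall is under 10% for any f up to 100%.

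**4. With a shared reference point.** If score and anchor both start just before the treatment being evaluated, f = 0 and the ratio is 1. If Week 12 is also counted from treatment, D drops out.

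**The case against.** The strongest reply is that analysis detail belongs in the SAP, to which the protocol refers and which is not at hand. The sentence at issue sits in a procedures section and may only say which scores are collected. This stands for omissions. It does not answer a reference point that the protocol itself states: an SAP that used another one would have to depart from that sentence.

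The evidence that men may be treated before baseline is also open to a milder reading. The formal criterion asks for planned treatment, and a returning patient may be a known patient with a new plan. The follow-up wording could cover a short lag between a prescription and the baseline questionnaires, with almost no gain in between. The PGI-I is only paraphrased, and men may take it to refer to the treatment now being started. All of this is fair. It limits the likely size, but it does not make the two reference points the same.

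A reader might infer more than the documents support:

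- *That the MID is shown to be biased by a known amount.* The shares in the tables are assumptions, and the formula presumes a mean-change method that the protocol does not specify.
- *That the crossover text proves medication at baseline.* It describes surgical-arm men at the time they are moved because surgery was not completed, not at enrolment.
- *That PGI-I ratings given before surgery corrupt the MID.* The wording on timing would include Preop, but the cell marks of Table 2.2 were not readable in the text available. The MID sentence uses Week 12 scores in any case, so a preoperative rating is not their natural anchor.
- *That crossover is a separate contradiction.* The timeline restarts and no new baseline score is named. That is mostly missing detail, which one clause can supply.
- *That the primary MID must be limited to men untreated at baseline.* This is a debatable trade-off, because Procedures Involved aims for a sample roughly representative of BPH patients.

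**Conclusion.** The point holds as a mismatch in stated text. The score change is tied to study baseline, the anchor to the time before treatment, and other sections allow these to differ. The Week 12 clock is also labelled in two ways, and the eligibility wording on current treatment is in tension with itself.

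The consequence depends on the reading. Taken literally, men who wait 12 weeks or more for surgery contribute no postoperative change at the nominal visit. On the more natural post-procedure reading, only drift between Baseline and Preop is left. For men who improved on treatment before enrolment, the MID tends to be too small. That direction rests on their rating the whole course of treatment and on similar total gains in both groups. The size cannot be derived from the protocol and may be small. The point should be fixed because the correction is cheap, not because a large bias has been demonstrated. Confidence is medium.

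**What to change.** In the MID text of Procedures Involved:

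- Define the MID change as the LURN SI score at Week 12 after treatment (after the procedure in the surgical arm) minus the last in-study score before the treatment being evaluated. That is Preop where it was completed, otherwise baseline, and for crossovers the last score before the switch.
- Pair this change with the PGI-I from the same Week 12 visit.
- Flag men already on BPH medication at baseline, and report the MID with and without them as a sensitivity analysis. Keep the primary set unrestricted.

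Reconcile the Week 12 clock between the MID text and the compensation table. Reconcile inclusion criterion 3 with Recruitment Methods on whether men already under treatment are eligible. Which rule is intended is for the sponsor to state.

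The cost is a few sentences and a little extra analysis. Preop and Week 12 are already in the schedule. Data Management and Confidentiality already lists the date of surgery and current medications, with extraction at baseline and follow-up. It lists no medication start date, so the flag cannot by itself separate long-standing treatment from a prescription issued just before baseline. Recording that date would sharpen the sensitivity analysis.

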## STUDY TIMELINES

For Aims 1 and 2, participant recruitment is expected to take 2 years, with each participant followed for 24 weeks from the latter of baseline or treatment initiation. Participants that crossover into different arms will be followed for 24 weeks within their most recent arm.

The first phase of the study is expected to last 12 months.

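### The protocol names only a 12-week score change for the minimally important difference (MID) and gives the other PGI-I/score pairs, including Week 24, no stated role in it

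*Protocol*

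**What the plan says.** Under Objectives, Aim 2 states that "multiple longitudinal assessments provide quantitative estimates of minimally important differences (MIDs"). It also plans effect sizes for the two indices between baseline and follow-up, without naming a week.

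Procedures Involved, in the text after Table 2.2, begins its MID paragraph with the anchor: "To assess MIDs, we will administer the PGI-I as a measure of global change at each post-baseline time point". The PGI-I asks men to compare their condition now with their condition before treatment. The paragraph then names the score change: "LURN SI-29 and SI-10 scores at 12 weeks post-baseline will be used to assess changes in scores since baseline".

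Table 2.1 (medical) and Table 2.2 (surgical) both run to Week 24. Study Timelines agrees, "with each participant followed for 24 weeks from the latter of baseline or treatment initiation". Study Endpoints lists MIDs as the Aim 2 endpoint and assigns the repeated symptom scores to Aim 1: "Serial symptom data will be collected over time using the LURN SI-29 (which includes the LURN SI-10 items) and the AUA-SI". The protocol refers the statistical analysis to a separate SAP, which was not available for this review.

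**The concern.** An anchor-based MID needs a PGI-I rating and a score change at the same visit. The protocol schedules the anchor repeatedly and says it does so for the MIDs, but names a score change at only one visit. A reader cannot tell whether Week 12 is the main time point with others in support, or the only one intended.

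Three things are at stake:

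- **Stability over time.** The Objectives (Aim 3) and Procedures Involved both expect transient symptoms after surgery, so time since treatment may affect the MID. A Week 12 figure alone does not show whether the MID holds at the end of follow-up.
- **Missing Week 12.** A man without a Week 12 assessment has no stated MID contribution, even if he has complete pairs at other visits.
- **Choice after the fact.** If the roles of the time points are not stated in advance, several MIDs can be computed and one preferred once the results are known.

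**Working it through.** The protocol gives no sample size, standard deviation or anchor correlation for the MID, so there is no planned figure to reproduce. The check has two parts.

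**1. The passages side by side**

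| Place in protocol | What it gives for the MID |
|---|---|
| Objectives, Aim 2 | Several follow-up assessments |
| Procedures Involved, anchor sentence | PGI-I at all points after baseline |
| Procedures Involved, score sentence | LURN SI change at 12 weeks |
| Study Timelines | 24 weeks of follow-up |

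Column headings of the schedules:

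- Table 2.1 (medical): Weeks 4, 8, 12, 16, 20 and 24, which is 6 points after baseline.
- Table 2.2 (surgical): Weeks 1, 2, 4, 6, 8, 12 and 24, which is 7 postoperative points, plus a preoperative one.
- Table 2.3 (SGM sub-study): Week 12 only.

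The score change is thus named at 1 of 6 medical points and 1 of 7 postoperative points. The cell marks of Tables 2.1 and 2.2 are not legible in the text at hand, so the anchor's timing is taken from the sentence and not from the tables. Week 12 is the only follow-up week common to all three schedules. Week 24 is common to both main-study schedules.

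**2. Illustrative precision**

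Assume that each man supplies a usable pair at each of k visits, with equal variance, one common correlation ρ between visits and the same true MID throughout. Relative to one visit, the standard error is then multiplied by

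sqrt((1 + (k − 1)ρ) / k).

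The values of ρ are assumptions; the protocol gives none.

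| Visits used | ρ | Ratio | Reduction |
|---|---|---|---|
| Weeks 12 and 24 (k = 2) | 0.5 | sqrt(1.5/2) = 0.866 | about 13% |
| Weeks 12 and 24 (k = 2) | 0.7 | sqrt(1.7/2) = 0.922 | about 8% |
| All six medical points (k = 6) | 0.5 | sqrt(3.5/6) = 0.764 | about 24% |
| All six medical points (k = 6) | 0.7 | sqrt(4.5/6) = 0.866 | about 13% |

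The k = 6 rows apply to the medical stratum only (up to 225 of at most 350 men).

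**The case against.** The strongest reply has four parts.

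- **The sentence does not exclude other visits.** It names 12 weeks without saying that no other visit will be used, and the same paragraph ties the anchor at every point to the MIDs. This stands. A reader might infer that the MID is restricted to Week 12, but the text does not say so. What it lacks is any statement of how the other pairs enter.
- **Week 12 is a sound choice.** It is the one follow-up week shared by both main schedules and the SGM sub-study, it lies later than the Weeks 1 to 8 postoperative assessments, and it asks for shorter PGI-I recall than Week 24. This stands too, and it is why Week 12 should remain the main time point.
- **The rest belongs in the SAP.** Model form and missing-data handling do, and the SAP may already use the further pairs. But the protocol itself names a time point, and that sentence sits uneasily with its own aim. An SAP that followed the sentence alone would fall short of Aim 2; one that used every visit would go beyond the sentence. A clarification in the protocol is warranted in either case.
- **The precision figures are hypothetical.** This stands. Men move between PGI-I categories, so the group choosing a given category changes from visit to visit and the real gain could be larger or smaller. The formula also assumes one MID across visits, which is the very thing that needs checking.

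**Conclusion.** The mismatch is real but modest. Aim 2 and the anchor schedule point to MIDs from several visits, while the only score change named is at 12 weeks, so the protocol leaves the other pairs without a stated part in the MID.

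Two stronger conclusions might be drawn, and the document supports neither. The first is that the other data, including Week 24, go unused: Study Endpoints uses the serial LURN scores for the Aim 1 trajectories. The second is that the trial cannot examine the MID at Week 24: the anchor is to be collected after baseline at every point, and nothing bars that analysis.

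The gain in precision cannot be derived from the protocol. The ranges above depend on exchangeable repeats from the same men and on assumed correlations of 0.5 to 0.7, and they only indicate scale. The conclusion rests on the inconsistency between the passages. The change is worth making because MIDs are a named endpoint and the repair is cheap.

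**What to change.** Amend the score-change sentence in the MID paragraph of Procedures Involved to state that:

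- the main MID estimate uses score changes from baseline to Week 12, paired with the PGI-I from the same visit;
- the MID is also estimated at Week 24 in the same way;
- a supportive repeated-measures estimate uses all post-treatment PGI-I/score pairs and allows for correlation within a man;
- results are reported by time point and by medical or surgical stratum.

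Model details can stay in the SAP, which should be checked against the amended text.

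The cost is one amended sentence and some extra analysis, with no new data and no added burden on participants. The downside is that PGI-I recall is longer at Week 24, so the MID there may differ for that reason alone. Reporting the two time points separately makes any such difference visible, and Week 12 remains the main result.
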